ISM	Independent Safety Monitor
MOP	Manual of Procedures
N	Number (typically refers to participants)
NIH	National Institutes of Health
OHRP	Office for Human Research Protections
OHSR	Office of Human Subjects Research
PI	Principal Investigator
QA	Quality Assurance
QC	Quality Control
SAE	Serious Adverse Event/Serious Adverse Experience
SOP	Standard Operating Procedure
US	United States

CONFIDENTIAL

This material is the property of the NYU School of Medicine and Langone Medical Center. Do not disclose or use except as authorized in writing by the study sponsor
Interventional Template Version: 11 January 2019

1 Introduction, Background Information and Scientific Rationale

1.1 Background Information and Relevant Literature

Anterior cruciate ligament (ACL) injuries are commonly seen and treated by orthopedic surgeons with approximately 400,000 reconstruction performed each year. Outcomes following ACLR are excellent with low rates of graft failure and high rates of return to pre-injury function. The surgery involves using a graft to replace the injured ACL in order to restore native knee biomechanics^{1,2}. There are many graft choices including bone-patellar-tendon-bone (BPTB), hamstring tendon or quadriceps autograft as well as several different allografts that the surgeon may choose from. Each graft has specific properties that contribute to surgeon choice. Graft-specific complications exist as well which further aid in the choice of graft.³

BPTB autograft is one of the most commonly used grafts worldwide especially in athletes and laborers. BPTB autograft is harvested through a midline incision over the patellar tendon that is carried down through the paratenon to expose the tendon³. Two parallel longitudinal incisions are made in the tendon to create a graft with the intended width. The incision is extended proximally to the distal pole of the patella where a segment of bone is removed in continuity with the tendinous insertion leaving a bone-void in the distal patella. Distally the incisions are carried down to the proximal tibia where a segment of bone is excised. The end product is a graft composed of tendon with bone plugs at both ends. The ACL reconstruction is then performed, incorporating the graft through femoral and tibial tunnels.^{4, 5}

Like all autografts, BPTB has the advantage of having ideal biologic compatibility. Unlike other grafts, BPTB includes bone plugs at both ends of the tendons. These bone plugs can be customized to have good fit within the femoral and tibial tunnels and further secured with interference screws or suspensory fixation. This leads to predictable healing and early biologic graft incorporation of as little as 6 weeks postoperatively^{4,5}. One of the advantages of the faster healing with BPTB autograft is that it allows for aggressive early rehabilitation. This results in earlier return to sport and pre-injury activity level⁵.

BPTB autograft is not without complications. One of the graft-specific complications associated with BPTB autograft is persistent anterior knee pain postoperatively^{3,4,5}. As a result, BPTB is often unsuitable for patients whose careers demand regular kneeling. Anterior knee pain can be a nuisance for patients and surgeons and in some circumstance be debilitating. The cause of anterior knee pain after ACLR has yet to be elucidated however the extensor tendon disruption and bone void from the harvest site is a likely contributory factor.

Currently, there is no consensus regarding management of the bone void after BPTB harvest. Existing literature is conflicting. Several studies report that bone grafting of the patellar defect can reduce the incidence of anterior knee pain and other complications, while Brandsson et al.⁶ demonstrated that grafting bone at the site of the harvest did not reduce anterior knee pain. At this institution all surgeons fill the patellar bone void. There is no agreement on the material used to fill the void with surgeons using autogenous bone graft, calcium phosphate cement and demineralized bone graft⁵.

Potential options for bone void filler include autologous bone graft, calcium phosphate cement, and demineralized bone matrix. Autologous bone graft is a byproduct of the customization of bone plugs during the BPTB autograft. In order to pass the graft through the tibial and femoral tunnels, the bone plug must be trimmed use bone cutters and other tools. The excess bone can be stored for use later in the operation for filling the bone defect of the patella. Autogenous bone graft is used often for its biologic compatibility and ability to incorporate into the bony defect. Most of the bone graft is cancellous bone which has osteogenic, osteoinductive and osteoconductive properties.

Calcium triphosphate is a bone-void filler used extensively throughout Orthopedic surgery. Calcium phosphate degrades slowly and is osteoconductive thereby new bone to replace it over time. Calcium

CONFIDENTIAL

This material is the property of the NYU School of Medicine and Langone Medical Center. Do not disclose or use except as authorized in writing by the study sponsor

Interventional Template Version: 11 January 2019

phosphate also has the highest compressive strength of synthetic bone grafts⁸. Calcium phosphate is commercially available and already used by the primary investigator as an option for filling the bone-void after the BPTB autograft harvest⁷.

Demineralized bone matrix (DBM) graft is another commonly used bone void filler used throughout orthopedic surgery. DBM has osteoinductive and osteoconductive properties that facilitate bony ingrowth. DBM is commonly used by surgeons at this institution to fill the bone void after ACL⁹.

1.2 Rationale

One of the common complaints after ACLR with BPTB autograft anterior knee pain. It is thought that this may be due to harvesting the patellar tendon for graft use. Specifically, this may be due to the bone defect that is left after graft harvesting. There is currently no consensus on a gold standard for treating the bone defect with surgeons using multiple commercially available bone void fillers as well as autologous bone graft in standard practice.

Potential Risks & Benefits

1.2.1 Known Potential Risks

The differing materials used will not prolong or significantly extend the time of surgery.

Possible adverse effects of using DBM include, but are not limited to: infection of soft tissue or bone, fever, deformity of the bone at the site of use, incomplete bone ingrowth, fracture of newly formed bone, hypercalcemia or transient hypercalcemia.

Possible adverse effects of using calcium phosphate cement include, but are not limited to: wound infection, wound dehiscence, fracture, loss of reduction, delayed or non-consolidation. While these risks are rare we will continue to monitor your condition to make sure these risks are minimized.

However, use of these elements are all considered standard of practice and used by surgeons at this institution and therefore, will not increase the level of risk for the patient beyond the normal surgery.

1.2.2 Known Potential Benefits

Potential benefits of being enrolled in this study may include reduced anterior knee pain after surgery. However, we cannot guarantee subjects will experience direct benefit as a result of participating in this study. We hope the knowledge gained from doing this study will inform surgeons in the future and, in turn, benefit other patients undergoing ACL reconstruction with BPTB autograft.

2 Objectives and Purpose

The purpose of the proposed study is to evaluate the effect bone-void filler on anterior knee pain following ACL reconstruction BPTB autograft.

2.1 Primary Objective

The purpose of the proposed study is to evaluate and compare the effect of three different bone-void fillers (autogenous bone obtained from graft preparation and bone plug customization; autologous bone plus DBM;

CONFIDENTIAL

This material is the property of the NYU School of Medicine and Langone Medical Center. Do not disclose or use except as authorized in writing by the study sponsor

Interventional Template Version: 11 January 2019

or autologous bone plus calcium phosphate cement) on anterior knee pain following ACL reconstruction BPTB autograft.

2.2 Secondary Objectives (if applicable)

Secondary outcomes include patient reported quality of life and functional outcome measures, rate (if any) of patella fracture, rate of return to activity, cost effectiveness and adverse events.

3 Study Design and Endpoints

3.1 Description of Study Design

This will be a single-center randomized controlled study. Patients will be randomized using RedCap using simple randomization. The study is comparing postoperative anterior knee pain after ACLR with BPTB autograft. There will be three cohorts that differ base on the bone-void filler used in the patellar boney defect. The three cohorts will include 1) autogenous bone obtained from the BTBPB graft harvest 2) Autologous bone plus demineralized bone matrix (Allosync DBM Putty, Arthrex, Naples, FL) and 3) autologous bone plus calcium phosphate cement (Quickset, Arthrex, Naples, FL).

3.2 Study Endpoints

3.2.1 Primary Study Endpoints

Primary endpoint will be based on the following postoperative surveys: KOOS, Kujala, IKDC, VAS for pain,

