9.1 Statistical Hypotheses

There is no difference in level of anterior knee pain, as defined by patient-reported functional outcome scores, between the three treatment groups.

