9.3 Description of Statistical Methods

9.3.1 General Approach

The general approach of this will be a 3-group study, without crossover. For descriptive statistics, categorical values will be described by percentages, and continuous variables will be described by means with standard deviations. To compare primary and secondary outcomes, an analysis of variance (ANOVA) will be performed, with a p-value of 0.05 set to determine statistical significance. Testing will be performed to determine whether sample distribution is normal; if not, non-parametric testing will be performed.

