9.3.2 Analysis of the Primary Efficacy Endpoint(s)

To compare primary outcomes (anterior knee pain), an analysis of variance (ANOVA) will be performed, with a p-value of 0.05 set to determine statistical significance. Testing will be performed to determine whether sample distribution is normal; if not, non-parametric testing will be performed. Patients who do not complete at least 80% of follow-up visits will be considered lost to follow-up and will not be included in the analysis.

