9.3.8 Multiple Comparison/Multiplicity

Not applicable.

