9.4 Sample Size

Based on an effect size of 0.25 with 3 cohorts, a total of 159 patients are needed with 53 in each group. Assuming a 15% drop-out/lost to follow up rate, each group will enroll 60 patients. Outcome measures will include patient reported outcomes: VAS, KOOS, Kujala, and IKDC. Additionally, we will report on rates of complications post-operatively, if any. Type I error rate (alpha) will be set at 0.05. Power will be set at 0.80.

10 Source Documents and Access to Source Data/Documents

Source data is all information, original records of clinical findings, observations, or other activities in a clinical trial necessary for the reconstruction and evaluation of the trial. Source data are contained in source documents. Examples of these original documents, and data records include: hospital records, clinical and office charts, laboratory notes, memoranda, subjects' diaries or evaluation checklists, pharmacy dispensing records, recorded data from automated instruments, copies or transcriptions certified after verification as being accurate and complete, microfiches, photographic negatives, microfilm or magnetic media, x-rays, subject files, and records kept at the pharmacy, at the laboratories, and at medico-technical departments involved in the clinical trial. It is acceptable to use CRFs as source documents. If this is the case, it should be stated in this section what data will be collected on CRFs and what data will be collected from other sources.

The study case report form (CRF) is the primary data collection instrument for the study. All data requested on the CRF must be recorded. All missing data must be explained. If a space on the CRF is left blank because the procedure was not done or the question was not asked, write "N/D". If the item is not applicable to the individual case, write "N/A". All entries should be printed legibly in black ink. If any entry error has been made, to correct such an error, draw a single straight line through the incorrect entry and enter the correct data above it. All such changes must be initialed and dated. DO NOT ERASE OR WHITE OUT ERRORS. For clarification of illegible or uncertain entries, print the clarification above the item, then initial and date it.

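### The primary endpoint spans four questionnaires and six visits with no named score, visit or success rule, so the stated alpha of 0.05 and power of 0.80 hold together only if one variable is fixed in advance

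*Combined protocol and SAP*

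**What the plan says.** **Endpoint.** Section 3.2.1: "Primary endpoint will be based on the following postoperative surveys: KOOS, Kujala, IKDC, VAS for pain". The sentence ends on a comma, so text may have been lost there. Section 3.2.2 adds no further secondary endpoints.

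**Timing.** Sections 6.1.1, 6.3.3 and 6.3.4 collect all four instruments at 1 week, 4-6 weeks, and 3, 6, 9 and 12 months. The visit schedule describes the four together as serving primary and secondary outcomes and does not say which is which.

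**Construct.** Section 9.1 tests "anterior knee pain, as defined by patient-reported functional outcome scores". Section 2.2 says "Secondary outcomes include patient reported quality of life and functional outcome measures", and 9.3.3 also treats functional scores as secondary.

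**Analysis.** Section 9.3.1: "To compare primary and secondary outcomes, an analysis of variance (ANOVA) will be performed, with a p-value of 0.05". Section 9.3.2: "To compare primary outcomes (anterior knee pain), an analysis of variance (ANOVA) will be performed, with a p-value of 0.05". Neither names an instrument or a visit.

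**Multiplicity.** "9.3.8 Multiple Comparison/Multiplicity Not applicable".

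**Sample size.** Section 9.4: "Based on an effect size of 0.25 with 3 cohorts, a total of 159 patients are needed with 53 in each group", and "Type I error rate (alpha) will be set at 0.05. Power will be set at 0.80". It then lists all four instruments as outcome measures.

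**The concern.** A type I error rate and a power belong to a defined decision rule, and here the rule is missing. Four instruments at six visits give 4 x 6 = 24 possible primary comparisons, each tested at 0.05. Two analysts following the plan faithfully could choose different comparisons and reach opposite primary conclusions from the same data.

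The consequence depends on the rule eventually adopted. If any favourable instrument or visit can support the claim, a chance difference could be reported as showing that a filler changes anterior knee pain. If all instruments must agree, false positives are controlled, but the trial is smaller than its stated power requires.

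The choice could also be made after scores have been seen. Section 7.5 provides for quarterly review of cumulative pain scores under the principal investigator's oversight and does not say whether they are shown by group.

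**Working it through.** **Inputs from the documents.** Three equal groups, effect size 0.25, alpha 0.05, power 0.80, 53 evaluable per group (9.4); four instruments (3.2.1); six post-operative visits (6.1.1).

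**Assumptions.** Section 9.4 does not say what kind of effect size 0.25 is; I take it as Cohen's f. The documents give no correlations, so I use 0.3, 0.5, 0.7 and 0.9.

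**Step 1: reproduce 9.4.** For a one-way ANOVA omnibus test:

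- Power = P[F'(2, N-3; λ) > F crit], where λ = N·f².
- N = 159: λ = 159 x 0.25² = 9.94, F crit(2, 156) = 3.054, power = 0.805.
- N = 156 (52 per group): power = 0.797.

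So 53 per group is the smallest size reaching 80%, and it matches 9.4 exactly. The calculation uses one value per patient: a score at one visit, or one summary over visits.

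**Step 2: independent tests, as an upper reference.** The chance of at least one false positive is 1 - 0.95^m. With m = 4 this is 0.185; with m = 24 it is 0.708.

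**Step 3: correlated tests.** Three-group ANOVAs were simulated on multivariate normal data with equal correlation, 53 per group, 20,000 trials. In the power row all four instruments truly have f = 0.25, with one group differing from the other two.

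| Rule | 0.3 | 0.5 | 0.7 | 0.9 |
|---|---|---|---|---|
| No effect: any of four instruments, one visit | 0.173 | 0.155 | 0.127 | 0.098 |
| No effect: one instrument, any of six visits | 0.246 | 0.210 | 0.164 | 0.110 |
| No effect: all four required, one visit | 0.0001 | 0.001 | 0.004 | 0.017 |
| Power: all four required, one visit | 0.499 | 0.555 | 0.615 | 0.704 |

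Evenly spaced group means give nearly the same power (0.505 to 0.702). With all 24 comparisons open, a separate simulation (10,000 trials) gave about 0.55 when the between-instrument and between-visit correlations are both 0.5, 0.39 when both are 0.7, and 0.26 when they are 0.9 and 0.8.

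**Step 4: four primary instruments with Holm.**

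- The first step uses alpha 0.05/4 = 0.0125. At N = 159, F crit = 4.507 and power per test = 0.624.
- After later steps, average power per test is 0.718 to 0.693 (correlation 0.3 to 0.9).
- The chance that at least one instrument succeeds is 0.931 to 0.748.
- With no true effect, the family-wise error is 0.047 to 0.028.

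**Step 5: sensitivity to the effect size.** At f = 0.20 with 53 per group, λ = 159 x 0.04 = 6.36 and power = 0.602.

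**The case against.** The best defence is that VAS is the implied primary endpoint. The primary objective and 9.3.2 concern anterior knee pain, 2.2 and 9.3.3 place functional scores among the secondary outcomes, and only VAS is labelled as a pain scale in 3.2.1. A multiplicity entry of not applicable would suit a plan with one primary outcome.

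This narrows the gap without closing it. Section 3.2.1 lists all four instruments as primary, and 9.1 defines pain through functional scores. Even with VAS granted, the visit is open: 4.5 mentions the one-year visit only as the length of participation, and the reference to final follow-up in 9.3.5 concerns baseline characteristics.

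Other objections have some force:

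- Alpha alone can be kept without a single variable, through Holm or by requiring all four to succeed. What cannot then be relied on is 80% power at 159. The conclusion is about alpha and power together.
- The inflated error rates illustrate an any-win rule that the plan does not state. They also assume equal correlation across visits and ANOVA throughout, although the plan switches to non-parametric tests if normality fails.
- Section 7.5 is a safety provision, and 9.3.6 plans no interim analysis. Nothing says scores will be used to choose the endpoint; the point is only that the text does not rule it out.
- The baseline of 53 per group favours the plan. Enrolling 60 with 15% loss leaves 51 per group, with power 0.788. That is a small and separate matter.

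**Conclusion.** The concern holds and must be fixed before outcomes are compared by group. The sample size in 9.4 fits one three-group ANOVA on one per-patient variable, and no section fixes that variable. The possible loss in 3.2.1 does not explain this, because 9.1, 9.3.2 and 9.4 could each have named a score and visit, and none does.

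For assumed correlations of 0.9 to 0.3 and 53 evaluable per group, the size is:

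- any of four instruments at one visit: about 10% to 17% false positives;
- VAS alone with six visits open: about 11% to 25%, or 16% at a correlation of 0.7;
- all four required at one visit: error under 2% when no instrument has an effect and never above 5%, but power only about 70% to 50% if all four truly have effect size 0.25.

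The exact figures depend on a success rule and correlations that the documents do not give. The conclusion does not: none of these rules delivers both stated figures at any correlation examined.

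**What to change.** **Preferred change.**

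- In 3.2.1, 9.3.2 and 9.4, name one score at one visit, or one pre-specified per-patient summary, as the primary endpoint. The choice is the sponsor's and must precede any comparison by group.
- State in 9.4 why an effect size of 0.25 is reasonable for that variable; no SD or difference is given now.
- Make its three-group omnibus test at 0.05 the only primary test, with pairwise filler comparisons only if it is significant. In simulation (40,000 trials) this gate held family-wise error at 0.049 with three equal groups and 0.052 with two equal and one different, which is 5% within simulation error.
- List the other instruments and visits as secondary in 3.2.2 and 9.3.3: Holm-adjusted, in a fixed order, or labelled descriptive.
- Bring 2.2 and 9.1 into line, and put this rule in 9.3.8.

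**Cost.** Wording and a justification; no new data. The 159 evaluable stand if 0.25 is supported, but at an assumed 0.20 power is 60.2%. The other instruments and visits can no longer support the primary claim.

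**If four primary instruments are kept.** State one visit and one of these rules, and restate the power in 9.4:

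- *(a) Any one may succeed, with Holm.* Power per test is 62.4% at the first step and about 69% to 72% after later steps. The chance that at least one succeeds is about 75% to 93% if all four truly have effect size 0.25.
- *(b) All four must succeed, each at 0.05 without adjustment.* Power is about 50% to 70%, and reaching 80% needs about 64 evaluable per group at correlation 0.9, rising to about 80 at 0.3.

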6.1 Study Procedures/Evaluations

6.1.1 Study Specific Procedures

- Medical history (i.e. mechanism of injury, acuity of injury, co-morbidities, smoking status) will be collected by the surgeon during the first office visit
- Physical exam (i.e. height, weight, range of motion, points of pain, ability to bear weight, and assessment of ligamentous laxity) will be performed during the first office visit
- Radiographic images (which may include an X-ray, computed tomography scan, and/or magnetic resonance imaging scan, may be obtain as part of standard of care, independent of this study, to confirm the presence of a torn ACL and search for any concomitant pathology)
- A discussion of if the results of any study specific procedures (e.g., radiographic or other imaging or laboratory evaluations) will be provided to participant.
- If the patient is eligible for the study (i.e. meets inclusion/exclusion criteria), he/she will be informed of the study, and asked if they would like to participate (if yes, consent will be obtained by the surgeon or a study member)
- Once consented, the following questionnaires will be administered: VAS, KOOS, KUJALA IKDC
- On day of surgery, surgeon will ensure patient is aware of their participation in the study, and will consent them for the procedure
- Intraoperatively, when appropriate, the surgeon will use the appropriate graft (autologous bone graft, DBM, or calcium phosphate) based on the group to which the patient was randomized
- The patient will return for post-operative visits at the following intervals: 1 week, 4-6 weeks, 3 months, 6 months, 9 months, and 12 months. During each post-operative visit, the patient will be asked to complete the same survey as completed preoperatively; if unable to obtain during the office visit, patients will be contact via phone within 2 weeks of the visit.

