6.3.4 Final Study Visit

Final Study Visit (12 months \pm 4 weeks)

- Record adverse events as reported by participant or observed by investigator.
- Obtain questionnaire for primary and secondary outcomes (VAS, KOOS, KUJALA IKDC)

CONFIDENTIAL

This material is the property of the NYU School of Medicine and Langone Medical Center. Do not disclose or use except as authorized in writing by the study sponsor

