9.3.3 Analysis of the Secondary Endpoint(s)

To compare secondary outcomes (functional outcomes scores, complication rates), an analysis of variance (ANOVA) will be performed, with a p-value of 0.05 set to determine statistical significance. For categorical variables, chi-squared testing will be performed. Testing will be performed to determine whether sample distribution is normal; if not, non-parametric testing will be performed. Patients who do not complete at least 80% of follow-up visits will be considered lost to follow-up and will not be included in the analysis.

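### Anterior knee pain is the trial's question, but the pain VAS is not anchored to the front of the knee or to kneeling, and no postoperative record of pain location is listed

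*Combined protocol and SAP*

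**What the plan says.** All references are to the combined protocol and SAP.

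- **Question.** Section 2.1 sets out to compare three fillers "on anterior knee pain following ACL reconstruction BPTB autograft". Sections 1.1 and 1.2 name the bone defect left by harvest as a likely contributor to that pain.
- **Endpoint.** Section 3.2.1: "Primary endpoint will be based on the following postoperative surveys: KOOS, Kujala, IKDC, VAS for pain". It names no item, subscale, pain location, activity or visit.
- **Hypothesis.** Section 9.1: "There is no difference in level of anterior knee pain, as defined by patient-reported functional outcome scores, between the three treatment groups".
- **Primary analysis.** Section 9.3.2: "To compare primary outcomes (anterior knee pain), an analysis of variance (ANOVA) will be performed". No score is assigned to the term.
- **Secondary analysis.** Section 9.3.3: "To compare secondary outcomes (functional outcomes scores, complication rates), an analysis of variance (ANOVA) will be performed".
- **Pain location.** It is named once, in the physical examination of section 6.1.1: "points of pain, ability to bear weight, and assessment of ligamentous laxity) will be performed during the first office visit".
- **Postoperative visits.** Sections 6.3.3 and 6.3.4 list adverse-event recording and the questionnaires. The final-visit entry reads "Obtain questionnaire for primary and secondary outcomes (VAS, KOOS, KUJALA IKDC".
- **Kneeling.** Section 1.1, having described persistent anterior knee pain, says: "As a result, BPTB is often unsuitable for patients whose careers demand regular kneeling". No kneeling rating is specified anywhere.

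**The concern.** The arms differ only in what fills the harvest defect, so the outcome of interest is pain at the front of the knee. The one instrument the protocol labels as a pain measure has no stated site. A patient asked for a general rating after this operation may report pain from elsewhere in the knee. Every patient has femoral and tibial tunnels (section 1.1). Imaging looks for accompanying pathology (section 6.1.1), and the exclusions in section 4.2 cover multiligament injury but do not name meniscal or cartilage lesions.

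Pain that the filler cannot affect adds variation without adding signal. If the VAS showed no difference, the reader could not tell whether the fillers perform alike or whether anterior knee pain was not measured closely enough. Location that is not recorded at a visit cannot be reliably recovered later.

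**Working it through.** **1. Is location captured after surgery?** The text, by time point:

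| Time point | Section | Pain location named? |
|---|---|---|
| First office visit | 6.1.1 | Yes, points of pain on examination, before any harvest |
| Day of operation | 6.3.2 | No; examination results are recorded without naming location |
| 1 week to 9 months | 6.3.3 | No; adverse events and four questionnaires |
| 12 months | 6.3.4 | No; adverse events and four questionnaires |

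**2. Which score stands for anterior knee pain?** Section 3.2.1 makes all four surveys primary. Section 9.1 defines the construct through functional scores. Section 9.3.2 calls anterior knee pain primary without naming a score. Section 9.3.3 places functional scores among the secondary outcomes, as does section 2.2. There are two readings:

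- If the functional scores are secondary, the VAS is what remains for section 9.3.2, and its location is not stated.
- If they are primary, no item or subscale is named as the anterior-knee measure.

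On either reading the plan does not specify how anterior knee pain is measured.

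**3. The plan's own sample-size figure.** Inputs from section 9.4: effect size 0.25, 3 groups, alpha 0.05, power 0.80, 53 per group (N = 159). I read 0.25 as Cohen's f, which is an assumption. For a one-way ANOVA the noncentrality is N × f² = 159 × 0.0625 = 9.94, on 2 and 156 degrees of freedom. Power is 0.805; with 52 per group it is 0.797. So 53 per group is the minimum, and the figure reproduces.

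**4. What dilution could look like (illustration only).** Two assumptions are needed, and the documents support neither: that f = 0.25 belongs to a front-of-knee rating, and that a share v of the variance of the general VAS comes from independent pain elsewhere. The arm differences stay the same while the variance grows, so the true standardised effect becomes 0.25 × √(1 − v). At N = 159:

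| v (assumed) | f | Power |
|---|---|---|
| 0 | 0.250 | 0.805 |
| 0.2 | 0.224 | 0.706 |
| 0.3 | 0.209 | 0.644 |
| 0.5 | 0.177 | 0.493 |

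The table shows the direction of the effect and how it depends on v. It is not an estimate for this trial.

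**The case against.** Several points on the other side stand, and they limit how far this can be taken.

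- **The VAS is not the sole route to the construct.** A reader might infer that it is the only pain scale and that harvest-site pain cannot be separated from other knee pain. The documents do not show this. Section 3.2.1 lists four surveys and section 9.1 defines anterior knee pain through functional scores. The content of KOOS, Kujala and IKDC is not reproduced, so it cannot be said that they lack anterior-knee items, or that the problem persists whichever score is chosen.
- **The VAS form is not in the file.** The missing anchor is a gap in the protocol text. The form that patients complete may already state a location.
- **A positive result is not undermined.** A reader might infer that a difference could not be attributed to the harvest site. Arms are randomised (section 3.1) and the filler goes into the harvest site (sections 5.2.1 and 5.3). Pain that the filler cannot change can dilute a difference; chance aside, it does not create one.
- **The loss of power is not established.** Section 9.4 does not tie 0.25 to any score. It may already be the effect expected on the listed instruments, in which case nothing would be left to attenuate.
- **Adverse events give partial capture.** Section 7.1.1 counts any symptom that appears or gets worse, so new anterior knee pain could be recorded at each visit, though not as a graded endpoint.
- **Kneeling.** A reader might infer that a patient who avoids kneeling would score near zero on the VAS. Section 1.1 links the complication to occupations that involve kneeling and says it can be debilitating. It does not say the pain vanishes without kneeling.

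None of this supplies a stated front-of-knee measure after surgery, or settles which score carries the primary analysis.

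**Conclusion.** The point holds in a limited form. As written, the protocol makes anterior knee pain its question, does not anchor the pain VAS to the front of the knee or to kneeling, and lists no postoperative assessment of pain location. Sections 3.2.1, 9.1, 9.3.2 and 9.3.3 also disagree on which scores are primary.

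The consequence is possible dilution of a between-arm difference on the VAS, and a null VAS result that is harder to read. This rests on one premise: that a general rating after this surgery picks up some pain the filler does not affect. The size of the dilution cannot be derived from the documents, and the power values in the illustration should not be cited as the trial's power. The change is worth making because it is cheap and bears directly on the primary question.

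**What to change.** 1. In sections 3.2.1 and 6.3.2 to 6.3.4, word the VAS as pain at the front of the knee. If the form already says so, carry that wording into the protocol.
2. In sections 9.1 and 9.3.2, name that single rating, at one stated visit, as the measure of anterior knee pain.
3. Add one self-report item on pain when kneeling, with a category for *does not kneel because of pain*. Use it from the visits at which kneeling is feasible, and analyse it as a supportive categorical outcome. Word it so that it can be answered by phone, since section 6.1.1 allows phone completion. That section also calls for the same survey before and after surgery, so it needs a line allowing for the later item.
4. Keep KOOS, Kujala and IKDC as collected, and reconcile sections 3.2.1, 9.1, 9.3.2 and 9.3.3 on which scores are primary and which secondary.

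Cost: a form change and about a minute more per visit, with no added visit or procedure. The downside is that a site-anchored VAS is less directly comparable with results from a general pain VAS.
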